Hematology, chemistry, and coags (10.7 mL) ⁸	X	X		X	X		X		
HLA-B27 Testing		X							
Urinalysis ⁹	X			X	X		X		
MARV antibody tests (2 x 10 mL) ¹⁰		X			X	X	X	X	X
Blood for research (100 mL) ¹¹								X	
PBMC/T-cell Assay ¹²		X			X		X		
Transcriptomics (2.5mL PaxGene RNA tube) ¹³		$X \times 2$	X	X	X	X			
MARV viremia (7 mL) and shedding ¹⁴		$X \times 2$	X	X	X	X	X		
Cytokine levels (10mL) ¹⁵		X		X	X		X		
Vaccination		X							
Post-vaccination observation ¹⁶		X							
Provision of emergency contact card		X							
Training and review of Memory Aid		X	X	X	X	X	X	X	X

Abbreviations: AESI = Adverse Event of Special Interest; eCRF = electronic case report form; HBsAg = hepatitis B surface antigen; HCG = human chorionic gonadotropin; Hct = hematocrit; HCV = hepatitis C; HepB = hepatitis B; HgB = hemoglobin; HIV = human immunodeficiency virus; INR = international normalized ratio; MAAE = medically attended adverse event; RBC = red blood cell; PBMC = peripheral blood mononuclear cell; PCR = polymerase chain reaction; PT = prothrombin time; PTT = partial thromboplastin time; SAE = serious adverse event; TEAE = treatment emergent adverse event; WBC = white blood cell.

Footnotes:

- ¹ Obtain written informed consent for participation in the clinical study, clinical samples, and HIV testing.
- ² Demographic data include age, height and weight (for BMI), race, and ethnicity.
- ³ Vital signs will include blood pressure and pulse while seated and at rest, and body temperature measured orally. On Visit 2, vital signs will be assessed up to 60 minutes before vaccination, then at 60-90 minutes after vaccination and at $6h \pm 1h$. (Shown as $X \times 2$)
- ⁴ Directed physical examination at discretion of Investigator. See the Protocol for the Arthritis Pathway algorithm for subjects with joint complaints. If rash is present on any visit, the PI should reference the Dermatology Pathway.
- ⁵ SAEs, MAAEs, and AESIs will be recorded from day of consent until EOS. AEs will be recorded beginning with Screening. All TEAEs will be recorded from dosing on day 1 through day 29, and during the rest of the study. Concomitant medications will be recorded up to 6 months prior to study entry and throughout the duration of the study. This will include dietary supplements and other prophylactic substances.
- ⁶ Pregnancy tests (serum HCG) will be done in all female subjects at Screening. Repeat pregnancy tests (urine) will be done in all female subjects prior to vaccination and at day 29.

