- ⁷ Screening serology will include HIV-1, HIV-2, HCV, and HBsAg.
- ⁸ Clinical laboratory assessments will include CBC (HgB, Hct, RBC, platelets), WBC with differential, metabolic chemistry panel, PT, PTT, and INR.
- ⁹ Urinalysis assessments by dipstick. Reflex testing by microscopy for abnormal blood or leukocyte esterase.
- ¹⁰ Two 10 mL tubes for serology: minimum of 6 (1.5 mL) aliquots of serum frozen. Four tubes will be used for viremia and neutralization studies and two tubes will be preserved at baseline and held for possible AE assessment. Collect one 10 mL tube for Rheumatologic or Dermatologic baseline
- ¹¹ Blood collection for serology and purification of IgG (100 mL). 10 × 10 mL SST tubes to be centrifuged, then the serum should be split as 10 mL aliquots in each of 5 x 15 mL conical sterile tubes and frozen at -60°C.
- ¹² Collect 6 × 10 mL EDTA tubes for PBMC separation and cryopreservation.
- ¹³ Collect in 2.5 mL PaxGene RNA tube for transcriptomics before dosing, then at 6h (± 1h) and on each subsequent visit as indicated.
- ¹⁴Blood (7 mL) for plasma, saliva (swab) and urine sample for virus detection before dosing, then at 6h (± 1h) and on each subsequent visit as indicated.
- ¹⁵ Blood (10 mL) for plasma cytokines, aliquoted into 4 × 1 mL cryotubes and frozen at -60°C.

Table 3: Blood Collection Volume Estimates

Blood Volumes	Volumes	D -28 to -1	Day 1	Day 2	Day 4	Day 8	Day 15	Day 29	Day 85	Day 181	Total
Blood for HepB, HepC, HIV (5 mL)	5.0	5.0									5.0
HLA-B27 testing	5.0		5.0								5.0
Safety Labs (10.7 mL)	10.7	10.7	10.7		10.7	10.7		10.7			53.5
Blood for MARV antibody tests (2 x 10 mL)	20.0		20.0			20.0	20.0	20.0	20.0	20.0	120.0
Blood for assay development (100 mL)	100.0								100.0		100.0
Blood for PBMC/T-cell Assay (6 x 10 mL)	60.0		60.0			60.0		60.0			180.0
Blood for RNA (2.5mL PaxGen tube)	2.5		2.5	2.5	2.5	2.5	2.5				12.5
Blood for viremia (7 mL)	7.0		14.0	7.0	7.0	7.0	7.0	7.0			49.0
Blood for Cytokine levels (10 mL)	10.0		10.0		10.0	10.0		10.0			40.0
	Totals	15.7	122.2	9.5	30.2	110.2	29.5	107.7	120.0	20.0	565.0

¹⁶ Includes TEAEs and examination of injection site 60-90 minutes after vaccination.

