5.1.2. Treatment Visit

Visit 2/Enrollment and Injection (day 1)

Subjects will have only 1 dosing visit during the study. Each subject will receive a 1 mL IM injection of PHV01 or placebo into the outer aspect of the subject's upper arm (deltoid area).

The following procedures will be performed during the injection visit, prior to the injection:

- Vital signs check
- Review of inclusion/exclusion criteria to confirm eligibility, then randomize
- Review of any AEs (including concomitant medications) since previous visit
- Directed physical examination (including proposed injection site)
- Rapid antigen test for SARS-CoV-2
- Urine pregnancy test (females only)
- Human leukocyte antigen (HLA) B27 typing (once only)
- Hematology, chemistries, and coagulation tests as above
- Collection of baseline samples for:
 - o PHV01 antibody, including sera for rheumatology and dermatology assessments
 - o PBMCs
 - o Transcriptomics
 - o Vaccinemia
 - Cytokines levels

Injection Procedures

- Administration of PHV01 or placebo
- Provision of emergency contact card
- Post-injection observation period: examination of injection site and vital signs check (≥60 minutes and ≤90 minutes post-vaccination)
- Explanation of the Memory Aid (see Section 5.4), distribution of thermometer and ruler, and review of use. Subjects are to record the severity of symptoms, including injection site reactions, joint-related AEs (joint pain, pain on motion of joints, joint swelling, joint tenderness), neurological issues, and rash, with the concomitant medications taken, and body temperature.

Subjects will remain in the clinic on day 1 for lunch and a blood draw at $6h \pm 1h$, including;

- Vital signs check
- Review of any immediate AEs or change in health status
- Collection of samples for vaccinemia, shedding, and transcriptomics

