5.1.3. Follow-Up Visits

Subjects will be followed closely in the first month in the clinic, then at 3 and 6 months as outlined below. They will use a Memory Aid with a list of graded solicited symptoms, including injection site reactions, self-recorded body temperature, and concomitant medications to help record any issues. There is space for unsolicited symptoms as well. This should be filled out daily until day 14, then 3 times a week until day 29, then once a week until day 181. Subjects should pay special attention to neurological symptoms, joint-related symptoms (joint pain, pain on motion of joints, joint swelling, joint tenderness) and rash.

If an AE of post-vaccination arthritis or rash is reported, the appropriate evaluations will be triggered as outlined in Section 6.2 and Section 6.3, respectively. Always swab an open skin lesion or aspirate vesicular fluid if present, along with oral mucosa. Swabs should be placed in Viral Transport Medium and frozen at < -60°C. The following procedures will be performed during each follow-up visit:

Visits 3-6/Interim Evaluation (days 2, 4, 8, and 15)

- Vital signs check
- Review of subject's AEs, concomitant medications, and any change in health status since previous visit including joint or neurological symptoms and rash
- Perform directed history and physical, including neurologic examination at discretion of the Investigator to assess possible AEs. Document abnormalities, including neurological, joint, or skin exam, signs if symptoms are present. Photograph rash if present.
- Hematology, chemistries, coagulation tests, and urinalysis as above (days 4 and 8 only)
- Collection of samples for:
 - o PHV01 antibody (day 8 and 15 only)
 - o PBMCs (day 8 only)
 - o Transcriptomics at each visit
 - o Vaccinemia and shedding at each visit
 - o Cytokine levels (days 4 and 8 only)
- At the day 4 visit, please remind subjects to call the site if they have any joint-related AEs, rash or neurologic complaints.

Visit 7/Final Acute Evaluation (day 29)

- Vital signs check
- Review Memory Aid for days 1-29
- Review of subject's AEs, concomitant medications, and any change in health status since previous visit including joint or neurological symptoms and rash
- Perform directed history and physical, as well as a neurologic examination. Document joint and skin exam if symptoms present. Photograph rash if present.
- Hematology, chemistries, coagulation tests, and urinalysis as above (days 4 and 8 only)

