4.4.5. Laboratory Data

Clinical laboratory values will be expressed in standard international (SI) units and results will be graded by the local laboratory as low, normal, or high. Additionally, select parameters will also be graded in accordance with the FDA document "Guidance for Industry: Toxicity Grading Scale for Healthy Adult and Adolescent Volunteers Enrolled in Preventive Vaccine Clinical Trials" outlined in Table 5-4 and Table 5-5. For analyses purposes, results not meeting grading criteria will be graded as Grade 0.

Descriptive statistics for serum chemistry, hematology, and coagulation values at baseline, all scheduled post-baseline visits, and the last study visit will be summarized for each clinical laboratory parameter. In the event of repeat values, the last non-missing value per study day/time will be used. Change from baseline (Day 1) will be calculated for each subject as the value at the specified post-baseline study visit minus the baseline value. The descriptive statistics for actual and change from baseline will include: the mean, standard deviation, median, and range of all values for each test.

Shift tables of change in toxicity grade for select laboratory parameters from baseline to each scheduled post-baseline visit and from baseline to last value on study will also be presented by dose level, all PHV01 dose levels combined and placebo. The numbers and percentages of subjects in each treatment group who had values below, within, and above the normal range at baseline and at the last visit will also be presented.

The results of rVSV PCR from blood, urine, and saliva will be tabulated by visit and treatment group.

All laboratory data will be provided in data listings. A subset listing will be presented for all toxicity graded laboratory values and abnormal laboratory values.

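### Two visit lists disagree with the Schedule of Events: the Day 29 list limits safety laboratories to Days 4 and 8, and the Day 1 pre-dose list omits the saliva and urine shedding samples

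*Protocol*

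**What the plan says.** **Day 29 laboratories.** In Protocol 5.1.3 the procedure list for Visit 7 (day 29) contains the item "Hematology, chemistries, coagulation tests, and urinalysis as above (days 4 and 8 only". The identical item stands in the list for Visits 3-6 (days 2, 4, 8 and 15), where the restriction fits. In Protocol Table 2 (section 3.2) the row "Hematology, chemistry, and coags (10.7 mL" is marked at Screening and Days 1, 4, 8 and 29. The urinalysis row (footnote 9: "Urinalysis assessments by dipstick") is marked at Screening and Days 4, 8 and 29. SAP Table 1-2 carries the same marks. In Protocol Table 3 the row "Safety Labs (10.7 mL" has 10.7 mL in the Day 29 column.

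**Pre-dose shedding sample.** In Protocol 5.1.2 the list under "Collection of baseline samples for" names antibody, PBMCs, transcriptomics, vaccinemia and cytokines. Shedding is named only in the 6-hour list: "Collection of samples for vaccinemia, shedding, and transcriptomics". Table 2 marks viremia and shedding twice on Day 1, and footnote 14 asks for "saliva (swab) and urine sample for virus detection before dosing" and again at 6 hours. The secondary safety endpoint in Protocol 3.1.2, and SAP 1.2.5.1 and 4.4.3, include urine and saliva results at Day 1, 0 hours.

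**The concern.** Sites often work from the visit-by-visit text and not from the grid. Here the two give different instructions at two points where a lost sample cannot be recovered later.

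Day 29 is the last scheduled laboratory visit, since Table 2 marks none at Days 85 and 181. Laboratory values are among the primary safety endpoints (Protocol 3.1.1). SAP 4.4.5 summarises every scheduled post-baseline visit and adds shift tables "from baseline to last value on study will also be presented by dose level". The interim analysis, run once all subjects have completed Day 29 and meant to guide dose selection for the next trial, includes descriptive laboratory statistics (SAP 3.12). Section 5.1.3 also serves as the outline for the final visit of a withdrawing subject (Protocol 4.6.1), so its lists have operational force.

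The 0-hour saliva and urine samples are each subject's own reference for the later RT-qPCR results. With a single dose there is no second chance to collect them.

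Protocol 10.4 allows no authorised deviations, so a site that follows one of two conflicting instructions departs from the other.

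**Working it through.** **Step 1. Reproduce Table 3.** Inputs are the row and column entries of Protocol Table 3.

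- Safety laboratory row: 5 draws (Screening, Days 1, 4, 8, 29) × 10.7 = 53.5 mL. Stated: 53.5.
- Day 29 column: 10.7 + 20.0 + 60.0 + 7.0 + 10.0 = 107.7 mL. Stated: 107.7.
- Grand total: 15.7 + 122.2 + 9.5 + 30.2 + 110.2 + 29.5 + 107.7 + 120.0 + 20.0 = 565.0 mL. Stated: 565.0.

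**Step 2. Repeat with the Visit 7 text taken literally (no Day 29 safety draw).**

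| Quantity | Table 3 | Without Day 29 draw |
|---|---|---|
| Safety laboratory row | 53.5 mL | 4 × 10.7 = 42.8 mL |
| Day 29 column | 107.7 mL | 107.7 − 10.7 = 97.0 mL |
| Grand total | 565.0 mL | 565.0 − 10.7 = 554.3 mL |

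None of the right-hand figures matches the plan. Table 3 was therefore built with a Day 29 draw and sides with Table 2 on the blood laboratories. It lists blood only, so it says nothing about urinalysis, or about saliva and urine for virus detection.

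**Step 3. Set the shedding passages side by side.**

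| Source | Day 1, before dosing | Day 1, 6 h |
|---|---|---|
| 5.1.2 visit text | vaccinemia; no shedding item | vaccinemia and shedding |
| Table 2 and footnote 14 | blood, saliva and urine | blood, saliva and urine |
| 3.1.2 endpoint; SAP 4.4.3 | urine and saliva at 0 h | urine and saliva at 6 h |

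The follow-up lists in 5.1.3 name vaccinemia and shedding together, so vaccinemia alone in 5.1.2 does not plainly cover saliva and urine. The one pre-dose urine item in 5.1.2 is a pregnancy test for females, which is not a virus-detection sample.

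**Step 4. Ceilings on what could be lost,** with 36 subjects and one saliva and one urine specimen per time point.

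- Laboratories: scheduled post-dose sets fall from 3 (Days 4, 8, 29) to 2, at most 36 × 1 = 36 sets.
- Shedding: time points fall from 7 (0 h, 6 h, Days 2, 4, 8, 15, 29) to 6, that is from 14 to 12 specimens per subject, at most 36 × 2 = 72 specimens.

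**The case against.** The best reply is that these are clerical slips which the documents themselves resolve. The Day 29 line is evidently carried over from Visits 3-6; under a Day 29 heading it defeats itself, since nobody lists a procedure in order to exclude it. Protocol 3.2 points to Table 2 for the schedule of assessments, and Table 3 and SAP Table 1-2 agree with Table 2. The shedding gap is an omission: 5.1.2 does not forbid a pre-dose sample, and footnote 14 requires one. All of this stands, and it lowers the chance of loss. It does not make the instructions agree.

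A reader might infer more than the documents support:

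- *That Day 29 laboratories or baseline shedding samples will not be collected.* The documents show conflicting instructions. They do not show which one a site will follow, so 36 and 72 are upper limits.
- *That the last laboratory value would be Day 8 for some subjects and Day 29 for others.* That needs staff to apply different passages to different subjects, and nothing in the plan suggests it.
- *That change to the last visit is itself the primary endpoint.* Protocol 3.1.1 names normal and abnormal laboratory values; change and shift are summary tables in Protocol 7.5.1 and SAP 4.4.5.
- *That without a 0-hour sample a false positive could not be told from early shedding.* Placebo recipients are sampled on the same schedule and show background positivity at group level. SAP 4.4.3 reports shedding time point by time point without baseline adjustment. What would go is confirmation within the subject.

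**Conclusion.** The point holds as an internal inconsistency that should be corrected. The design is not in question. The Visit 7 laboratory item conflicts with Table 2, SAP Table 1-2 and, for blood, Table 3. The pre-dose list in 5.1.2 is incomplete against footnote 14 and the 0-hour endpoint. The two differ in strength: the first is an explicit restriction that contradicts the schedule, the second an omission.

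The exposure is at most 36 Day 29 laboratory sets (one of three scheduled post-dose sets per subject) and at most 72 pre-dose saliva and urine specimens. These ceilings assume 36 dosed subjects and a site that follows the visit text in every case; the documents give no basis for a likelihood. It merits more than an editorial note, because the laboratory loss would fall on the last scheduled set for a primary safety endpoint and on the interim analysis. The 0-hour loss would leave no within-subject baseline for shedding.

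**What to change.** Reconcile Protocol 5.1.2 (pre-dose sample list) and 5.1.3 (Visit 7 laboratory item) with Table 2, footnote 14 and the endpoints and, for the blood laboratories only, with Table 3, so that the visit text and the Schedule of Events give the same instruction. The sponsor should state which passage governs each item.

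If the Schedule of Events governs, the cost is two wording corrections in the visit text, with no added visit or blood volume. If the visit text governs, the consequences run further: Table 2, SAP Table 1-2 and the Table 3 totals would have to change, as would the 0-hour urine and saliva time point in Protocol 3.1.2 and the SAP, and the analyses that use Day 29 laboratories.

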5.1.4. Early Termination Visits

Subjects who withdraw from the study for any reason between scheduled study visits will be asked to complete assessments for the next scheduled visit (at least 28 days after dosing) as their EoS Visit.

5.1.5. Biological Samples

Samples collected under this protocol will be used to conduct protocol-related safety and immunogenicity evaluations related to the vaccine. Immunological testing will be performed at a specialty laboratory that does not have access to the randomization code group assignment.

All specimens for clinical laboratory testing will be collected at the site and processed by the site. The amount of blood to be drawn, by visit, is provided in the study-specific laboratory manual and in Table 3.

All samples will be collected using standard techniques and safety precautions. To maintain clarity and confidentiality, specimens will be labeled with at least the collection date and the applicable study ID code for the subject. Labels may be in barcode format or handwritten.

If necessary, biological samples will be stored temporarily at the site to await transport to appropriate laboratories for processing and analysis. Transport and storage of these biological samples will be handled according to applicable SOPs/SSPs and instructions in the Sponsor-approved laboratory manual.

Any study for the future use of these biological samples that are not identified in this protocol shall have IRB approval. In addition, a subject may decide at any point to withdraw consent for the future use of his/her samples. Should a subject withdraw consent for the use of his/her samples, any unused samples will be destroyed. All other study subject samples will be transported to PHV or designee and stored indefinitely. Samples will be stored in a locked, controlled-access freezer.

5.2. CONCOMITANT MEDICATIONS

The restrictions on the use of concomitant medications by subjects apply through day 29 only and include immunosuppressive medications, including oral or injected corticosteroids.

Drugs that are used to reduce fever and pain are generally not allowed 24 hours before injection or 24 hours after injection. This protocol places no restrictions on rescue medications, and the Investigator will recommend medication for symptomatic relief if necessary.

5.3. CONTRACEPTIVE GUIDANCE AND COLLECTION OF PREGNANCY INFORMATION

All subjects must be willing to minimize blood and body fluid exposure of others until six or eight weeks after dosing by:

- Using effective barrier prophylaxis, such as latex condoms during penetrative sexual intercourse or oral sex with opposite-sex or same-sex partners (until eight weeks after dosing)
- Abstaining from sexual activity, including oral sex, if effective barrier prophylaxis cannot be used (until eight weeks after dosing)
- Avoiding the sharing of needles, razors, or toothbrushes (until six weeks after dosing)
- Avoiding open-mouth kissing (until six weeks after dosing)
- Covering of any open-skin lesions (until six weeks after dosing)

5.3.1. Woman of Childbearing Potential

A woman is considered fertile following menarche and until becoming postmenopausal unless permanently sterile (see below). If fertility is unclear (e.g., amenorrhea in adolescents or athletes) and a menstrual cycle cannot be confirmed before first dose of study intervention, additional evaluation should be considered.

Premenarchal or premenopausal women with one of the following surgical histories are not considered to be women of childbearing potential:

- Documented hysterectomy
- Documented bilateral salpingectomy
- Documented bilateral oophorectomy

For individuals with permanent infertility due to an alternate medical cause other than the above, (e.g., mullerian agenesis, androgen insensitivity), Investigator discretion should be applied to determining study entry. *Note: Documentation can come from the site personnel's review of the participant's medical records, medical examination, or medical history interview.*

5.3.2. Postmenopausal female

A postmenopausal state is defined as having no menses for 12 months without an alternative medical cause. This can be documented by:

- A high follicle stimulating hormone level in the postmenopausal range may be used to confirm a postmenopausal state in women not using hormonal contraception or hormonal replacement therapy. However, in the absence of 12 months of amenorrhea, confirmation with more than 1 FSH measurement (> 35 IU/L or mIU/mL) is required.
- Females on hormone replacement therapy and whose menopausal status is in doubt will be required to use one of the non-estrogen hormonal highly effective contraception methods if they wish to continue hormone replacement therapy during the study. Otherwise, they must discontinue hormone replacement therapy to allow confirmation of postmenopausal status before study enrollment.

5.3.3. Contraception Guidance

If a subject is sexually active or becomes active, then she and her male partner must use a male or female condom in addition to one of the following effective methods of adequate contraception until eight weeks after dosing. Highly effective birth control includes the following methods:

- Coil (intrauterine device)
- Oral contraceptive pill containing combined estrogen and progesterone
- Depot progesterone injections
- Progesterone implant
- Vaginal ring
- Transdermal patch containing combined estrogen and progesterone

